Half of the hospitalized patients will be monitored with POC testing and non blinded CGM (for both the investigators and the subjects, **Intervention Group**). Management of this group of patients will be based on glucose values obtained by CGM and POC testing.

Half of the subjects will be monitored by POC testing only. CGM results will be blinded (for both the investigators and the subjects, **Control Group**). Management of this group of patients will be based on glucose values obtained by POC-FSBG only.

Aim 1: To determine if we can prevent more hypoglycemic values/ events in the Intervention Group vs Control group.

Hypothesis 1: CGM use (un-blinded) and POC-FSBG will prevent more hypoglycemic values/events compared to subjects that we will be managed by POC-FSBG only.

Aim 2: To determine if subjects that are in the Intervention Group will have decreased hyperglycemia compared to control Group.

Hypothesis 2: Subjects that will be managed by CGM and POC-FSBG will have decreased hyperglycemia compared to subjects that will be managed by POC-FSBG only.

Aim 3: To determine if subjects that are in the Intervention Group will have decreased severe hyperglycemia compared to control Group.

Hypothesis 3: Subjects that will be managed by CGM and POC-FSBG will have decreased severe hyperglycemia compared to subjects that will be managed by POC-FSBG only.

C. Design and Methods:

Human Subjects

Inclusion criteria: \geq 21 years of age; history of type 2 DM managed with insulin (either basal bolus, basal with per os DM medications) who also fulfill 1 or more of the following criteria, all known risk factors of hypoglycemia [31-34]: Insulin use of more than 0.6 u/kg, age \geq 65, BMI \leq 27, renal failure, liver failure, active malignancy, congestive heart failure, CVA or sepsis. We will also include hospitalized individuals with type 2 DM treated with insulin that developed a significant hypoglycemic episode in a recent (<6 months) hospitalization.

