Exclusion criteria: Subjects that have a history of type 1 DM. History of type 2 DM that are being treated with diet or any combination of oral antidiabetic drugs only, as these patients are less likely to benefit from CGM use. We will also exclude subjects that have significant hyperglycemia or DKA that requires treatment with intravenous insulin infusion and any patients that need hospitalization in the critical care (ICU) setting. Pregnant patients, patients receiving glucorticoids in doses (equivalent) to \geq 20 mg of hydrocortisone/day, or patients that are expected to require a hospital stay <3 days will also be excluded [35]. Finally, we will exclude any individual with a mental condition rendering the subject incapable of understanding the objectives and potential consequences of the study.

The ethics committee of the University of Maryland and VABMC will approve the study protocol. Informed consent will be obtained from all enrolled subjects.

Lab Values and Glucose Measurements:

All participants will have an Hba1c, CBC and BMP at the time of enrollment in the study, lab values that represent standard of care in admitted subjects with DM.

For DM subjects monitored with POC-FSBG and CGM (**Intervention Group**) or with POC-FSBG only (**Control Group**): In both groups, participants will have their glucose values monitored with POC-FSBG as follows: Pre-breakfast (fasting), pre-lunch, pre-dinner, at bedtime and at 3am) [6, 36]. For admitted veterans that are not eating or that receive continuous enteral nutrition, we will check POC-FSBG every 6 hours [15].

For DM subjects enrolled in the POC-FSBG and CGM (**Intervention Group**), in addition to POC-FSBG, glucose values will be monitored continuously, over 24 hours, by CGM.

POC-FSBG will be measured any time the CGM alarms. In addition POC-FSBG will be measured any time a participant (in either group) develops symptoms that are suggestive of hypoglycemia.

Insulin Treatment:

Titration of insulin will be not made based on the CGM values. Titration adjustments of the insulin regimen will be made by the inpatient diabetes management service team, based on POC-FSBG values. Titration of basal insulin (glargine) will be made based on the fasting am glucose values, based on the following algorithm (**Table 1**).

Table 1. Titration of basal insulin (glargine) [35]			
Fasting am BG values	Basal dose (IGIa) adjustments		
If BG< 60 mg/dl	Decrease dose by 20%		
If BG 60-79 mg/dl	Decrease dose by 10%		

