Treatment of hypoglycemia will be similar in the 2 groups and will be based on standard hospital protocols.

Outcome Measures

Aim 1: Hypoglycemic values will be defined as POC-FSBG<70 mg/dl and will be classified as severe if it involved loss of consciousness and/or seizures [35] We will evaluate if there is a difference in the total number of hypoglycemic events between the 2 groups, by evaluating POC BG values. Time spent during hypoglycemia will be also calculated in both groups, using data from GCM devises.

Aim 2: We will compare time spent in hyperglycemia (>180 mg/dl) between the 2 groups. We will compare glucose values obtained from the CGM devises from Interventional group (unblinded) and Control group (blinded).

Aim 3: We will compare time spent in severe hyperglycemia (>300 mg/dl) between the 2 groups. We will compare glucose values obtained from the CGM devises from Interventional group (un-blinded) and Control group (blinded).

Statistical plan

Descriptive statistics including means and SDs will be computed for continuous variables, and counts and proportions will be computed for categorical variables. Wilcoxon's rank sum test will be applied to comparing continuous variables between the intervention group and the standard-of-care group. Fisher's exact test will be used to compare categorical variables between the two groups. Data analysis will be carried out using SAS statistical program.

Safety

All subjects that participate in the proposed study will be patients with DM that will be admitted to the VABMC hospital for medical reasons. Glucose monitoring for **Control group** will be made with POC-FSBG testing that represents standard of care. **Interventional group** will be monitored as above, however additionally CGM will be utilized. To address any daytime or overnight problems the PI will be on call. The PI is well versed in trouble shooting problems with the CGM devices. Nurses and house staff will receive additional training for the CGM devices.

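### Aims 1 to 3 compare totals of events and time with no denominator or observation window, although length of observation will vary between patients

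*Combined protocol and SAP*

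**What the plan says.** The aim is to "prevent more hypoglycemic values/ events in the Intervention Group vs Control group". Outcome Measures makes this operational as a "difference in the total number of hypoglycemic events between the 2 groups", taken from POC readings. The threshold is set for single readings: "Hypoglycemic values will be defined as POC-FSBG<70 mg/dl". CGM adds a further quantity: "Time spent during hypoglycemia will be also calculated in both groups, using data from GCM devises".

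The other two aims rest on CGM in both arms. Aim 2: "We will compare time spent in hyperglycemia (>180 mg/dl) between the 2 groups". Aim 3: "We will compare time spent in severe hyperglycemia (>300 mg/dl) between the 2 groups".

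On analysis, the Statistical plan says "Wilcoxon's rank sum test will be applied to comparing continuous variables between the intervention group and the standard-of-care group", with Fisher's exact test for categorical variables. It has no rate, offset or other adjustment for exposure.

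The only limit on length of observation is in the exclusion criteria: "patients that are expected to require a hospital stay <3 days will also be excluded". No maximum stay, CGM wear period, or start or end of observation is given. The Safety section adds that CGM comes off for MRI and CT, so recorded CGM time can be shorter than the stay.

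**The concern.** The aims ask whether glycemia is better under unblinded CGM. A total of events or hours answers that only if patients are observed for similar lengths of time. Here they will not be, and a patient who stays longer has more opportunity for every outcome.

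Three things are at stake. Variation in stay adds noise, which a small study can ill afford. If mean stay differs by arm, totals differ even when the daily rate does not; stay is determined after randomisation, and the Background says that the intervention may improve it. And the pilot is meant to inform larger studies, but a total over an unstated period does not transfer to a trial with different stays. Because the form of the outcome is unstated, it could also be settled after the data are seen.

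Separately, the plan defines a low reading but gives no rule for grouping several low readings into one event, so the count itself is not fully defined.

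**Working it through.** The plan has no sample size, power or event rate, so there is no figure of its own to reproduce.

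**Exposure, from the protocol's own schedule.** Eating patients have 5 scheduled POC tests a day; CGM runs 24 hours a day.
- 3-day stay: 5 × 3 = 15 tests and 24 × 3 = 72 CGM hours.
- 7-day stay: 5 × 7 = 35 tests and 24 × 7 = 168 CGM hours.

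At the same daily rate, the second patient is expected to show 7/3 = 2.33 times the total of the first.

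**Expected ratio when stay differs by arm.** With a common daily event rate r, the ratio of expected totals is (r × stay in Intervention) / (r × stay in Control). At 5 v 6 days this is 5/6 = 0.83; at 4.5 v 6 days it is 4.5/6 = 0.75. The daily rate ratio is 1 in both cases.

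**Simulation of the planned Wilcoxon test.** All inputs are assumptions: two-sided 5%; 40 per arm; stay = 3 days plus an exponential part, Control mean 6 days; fraction of time >180 mg/dl drawn from a beta distribution with mean 0.40 and concentration 5; hours = fraction × stay; events Poisson with gamma variation between patients (shape 1 or 2), 0.2 or 0.5 per day. Aim 1 is taken as a Wilcoxon test on per-patient counts, since the plan does not name its test.

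| Scenario | Totals | Percent of time or per day |
|---|---|---|
| Equal stays, no effect, hours >180 | about 5% | about 5% |
| Equal stays, 28% v 40% of time >180 (power) | about 64% | about 78% |
| Equal stays, event rate halved (power) | 40-71% | 42-77% |
| 5 v 6 days, equal daily event rate | about 7-9% | about 5% |
| 5 v 6 days, equal fraction of time >180 | about 14% | about 5% |
| 5 v 6 days, 28% v 40% of time >180 | about 89% | about 78% |

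Sensitivity:
- The 14% ranges over 8-22% as the beta mean varies over 0.25-0.55 and the concentration over 3-8. Varying the shape of the stay distribution instead gives about 10-18%.
- At 20 per arm, hours reject about 9.5% and counts 5.9-6.9%.
- At 5.5 v 6 days the effect is small: hours 6.6%, counts 5.3-5.8%.
- For sparse outcomes, such as time <70 or >300 with half of patients at zero, raw hours at 5 v 6 days reject 5.0-5.3%, or 6.4-7.0% if a longer stay also makes any excursion more likely.

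**The case against.** **Time spent could mean percent of time.** It could, and the plan does not commit to raw hours. The Aim 2 figures for hours are therefore conditional. What stands is that the form is unstated; for Aim 1 the wording does point to a total.

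**The CGM section sets a 24-hour window.** The phrase about monitoring over 24 hours under Lab Values and Glucose Measurements most naturally means round the clock. It is written for the Intervention Group and tied to no outcome.

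**Randomisation balances stay.** If it does, the test is valid and the cost is precision only. This is conceded. The Insulin Treatment section bars titration on CGM values and the high alarm is set at 400 mg/dl, which makes a one-day effect on stay less likely, although the Aims section describes CGM-based management more broadly.

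**A reader might infer a false-positive rate of about 14% for Aim 2, or that a shorter stay would conceal worse glycemia.** The second case can be constructed: with 50% v 40% of time >180 and 5 v 6 days, a difference is detected 11.5% of the time on hours and 57.1% on percent. But the Background presents better stay as a consequence of less hyperglycemia. It does not predict shorter stay with unchanged or worse hyperglycemia. On its own pathway, hours would exaggerate a real effect rather than create a false one.

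**A reader might also take the 15-minute retest as proof of double counting.** It is not. That retest follows a value of 70-85 mg/dl, which is not low under the plan's definition. Retesting after a low value falls under hospital protocols that are not shown. Only the missing grouping rule stands.

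**Conclusion.** The point holds as an avoidable weakness that should be fixed. Totals with no denominator or window answer a less precise question than the aims pose, and they become biased measures of daily glycemia if stay differs by arm.

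The part that needs no difference in stay is the loss of power: about 14 points for Aim 2 if hours are used (78 − 64), and about 2 to 6 points for Aim 1. With a one-day difference in mean stay and equal daily event rates, Aim 1 counts reject about 7-9%. Sparse outcomes stay near nominal. The larger Aim 2 figure requires both raw hours and a shorter stay without less hyperglycemia, so it should not be read as the plan's expected error rate.

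The textual omission is certain. The sizes rest wholly on the assumed sample size, stay and glucose distributions. No difference in CGM wear between arms is claimed.

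**What to change.** - State and record the start and end of observation, separately for POC and for CGM.
- Aim 1: analyse POC hypoglycemic events per patient-day of POC monitoring, one rate per patient, by Wilcoxon. Add a rule for when repeated values <70 mg/dl form one event; for example, an event lasts until a value of 70 or more is recorded.
- CGM outcomes: analyse percent of each patient's valid CGM time <70, >180 and >300 mg/dl, by Wilcoxon. Valid time can be the number of recorded 5-minute readings × 5 minutes.
- Report length of stay, POC-monitored days and valid CGM hours by arm.
- Add a sensitivity analysis restricted to the first 3 days.

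The cost is a few sentences, start and stop times in the data capture, and a little more analysis. No minimum-wear exclusion from the main analysis and no count model is needed.

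One limit should be stated. Percent over the whole stay is not fully protected if glycemia improves during the stay and stay differs by arm. Assuming time >180 falls from 60% toward 24%, it rejects 6.2-6.9% at 5 v 6 days and 7.6-10.8% at 4.5 v 6, against 4.8-5.4% over the first 3 days; hence the sensitivity analysis.

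The extra alarm-triggered POC tests in the Intervention Group are a separate issue, which a per-day rate does not correct.

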Several published studies have examined the use of CGMs in the inpatient setting [21-30]. Most of the studies have been performed in the ICU setting [21-28], where CGM use may not be beneficial to the patients, as patients are monitored closely, with glucose values checked every 1 hour or even more frequently. In the non-ICU setting, where the majority of patients are hospitalized (General Wards), the data for using CGM are limited. In a single arm observational study Burt and colleagues showed that CGM was able to detect for hyperglycemia excursions and more hypoglycemia events than POC-FSBG [29]. In a study that examined the use of CGM in hospitalized patients with DM2 [30], CGM use was able to detect more hypoglycemic events (55 vs 12, p=0.0001) compared to the group that was managed with POC-FSBG. 26.3% of the hypoglycemic events were asymptomatic and the majority of these events were identified by CGM use (86.7%). CGM use was more likely to detect nocturnal and daytime hypoglycemic events (p=0.0399 and 0.0066 respectively). Notably participants in this clinical trial [30] were insulin naïve (not previously on insulin) DM2 subjects, a group of patients that may not be at high risk for hypoglycemia. Both of these studies [29, 30] showed that CGM use can detect more hypoglycemic events. However, as these studies were blinded for both investigators and patients, interventions to prevent hypoglycemia were not performed. The next reasonable step is to examine whether CGM use can prevent hypoglycemic events.

In this pilot study we propose to examine the clinical use of CGM in hospitalized insulin treated patients with DM2, admitted in General Medicine Wards setting who are at higher risk for hypoglycemia. We anticipate that our intervention will decrease the number of hypoglycemic events, which represents a significant safety concern in the inpatient setting. We also anticipate that our intervention may decrease hyperglycemia (mild or severe) and therefore may improve clinical outcomes such as nosocomial complications and length of stay. This pilot study may lead us to obtain preliminary data that will help us to design larger clinical studies

B. Aims:

In this randomized clinical trial, we will evaluate whether inpatient use of CGM devices are beneficial in subjects with DM2 in the non-critical care setting (general wards).

Groups:

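### Aims 2 and 3 leave the enrollment HbA1c unused: a cheap precision gain of unknown size, worthwhile mainly for Aim 2

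*Combined protocol and SAP*

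**What the plan says.** - Lab Values and Glucose Measurements: "All participants will have an Hba1c, CBC and BMP at the time of enrollment in the study". The section describes these tests as standard of care, so they add no collection burden.
- Outcome Measures, Aim 2: "We will compare time spent in hyperglycemia (>180 mg/dl) between the 2 groups". Aim 3: "We will compare time spent in severe hyperglycemia (>300 mg/dl) between the 2 groups". Both use CGM data, unblinded in one arm and blinded in the other.
- Statistical plan: for continuous variables, Wilcoxon's "rank sum test will be applied to comparing continuous variables between the intervention group and the standard-of-care group"; for categorical variables, Fisher's exact test. No covariate, stratification factor or model is named, and HbA1c has no analytic role anywhere. Summaries are descriptive, with no between-arm estimate or confidence interval.
- Background and Significance: "This pilot study may lead us to obtain preliminary data that will help us to design larger clinical studies".
- The documents give no sample size, alpha, power, effect size or SD, and no correlation between HbA1c and either outcome. They do not say that each patient contributes one value to the test.

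**The concern.** In a small randomized trial, chance differences between arms in baseline glycemia add noise to a comparison of time in hyperglycemia. HbA1c is a baseline marker of glycemic control, already measured in everyone, and could remove some of that noise. The study hopes to inform larger trials, so a tighter estimate is useful. Fitting HbA1c would also show how prognostic it is in this population, which the design of a larger trial would need. Only efficiency is at stake. If one value per patient is analysed, the planned test holds its error rate.

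**Working it through.** The plan has no figure to reproduce, so every figure below rests on assumed inputs.

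**Inputs.** From the documents: two randomized arms, half of the patients in each, HbA1c in all, CGM outcomes for Aims 2 and 3. Assumed: two-sided alpha 0.05; 20 per arm (also 10 and 30); r from 0 to 0.5; a 0.65 SD shift; and 0%, 50% or 70% of controls with no time above the threshold.

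**Step 1, closed form for a continuous outcome.** Adjustment multiplies the variance of the arm difference by about (1 - r²) × (1 + 1/(N - 4)), where N is the total. The second factor is the price of one covariate.
- N = 40: the price is 1 + 1/36 = 1.028. The interval width ratio is √1.028 = 1.014 at r = 0, √(0.91 × 1.028) = 0.967 at r = 0.3 and √(0.75 × 1.028) = 0.878 at r = 0.5. Break-even r is √(1 - 1/1.028), about 0.16.
- N = 20: the price is 1 + 1/16 = 1.0625. The width ratio at r = 0 is √1.0625 = 1.031, about 3% wider. Break-even r is √(1 - 1/1.0625), about 0.24.

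**Step 2, simulation at 20 per arm.** There were 20,000 trials per cell, with a latent normal outcome, left-censored to create the zeros. The tie-corrected Wilcoxon test was compared with the t-test for arm in a regression of outcome rank on arm and HbA1c rank. Monte Carlo standard error of each power difference is at most 0.28 points.

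Change in power, in points:

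| Controls at zero | Wilcoxon power | r = 0 | r = 0.2 | r = 0.3 | r = 0.5 |
|---|---|---|---|---|---|
| none | about 49% | -0.7 | +0.7 | +2.8 | +9.9 |
| 50% | about 38% | 0.0 | +1.5 | +2.0 | +6.7 |
| 70% | about 29% | +0.2 | +0.6 | +1.3 | +3.4 |

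Width of the adjusted 95% interval for the mean difference, relative to unadjusted:

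| Controls at zero | r = 0 | r = 0.2 | r = 0.3 | r = 0.5 |
|---|---|---|---|---|
| none | 1.014 | 0.994 | 0.968 | 0.878 |
| 50% | 1.014 | 1.001 | 0.985 | 0.932 |
| 70% | 1.015 | 1.006 | 0.994 | 0.956 |

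The first row agrees with Step 1. With 70% zeros, part of the small power gain comes from the continuity correction in the Wilcoxon test. Without that correction the changes are about -0.5 at r = 0 and 0.2, +0.3 at r = 0.3 and +2.4 at r = 0.5.

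**Step 3, 30 per arm.** Across the three zero scenarios the power change is -0.3 to +0.1 at r = 0, +1.6 to +4.0 at r = 0.3 and +4.4 to +11.5 at r = 0.5.

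**Step 4, validity.** Over the 24 cells (2 sizes × 4 correlations × 3 zero shares), type I error was 4.6-5.0% for Wilcoxon and 4.7-5.3% for the adjusted rank test. At 20 per arm the model-based adjusted interval covered 94.6-95.1% with no zeros and 94.3-94.7% with 50% zeros, but 91.9-92.5% with 70% zeros. The unadjusted interval falls equally short there (91.9-92.4%), so the zeros are the cause. The rank test and the mean-difference interval disagreed on significance in 6-9% of trials without zeros and 15-20% with 50-70% zeros.

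**The case against.** The strongest case against is that this is optional. An unadjusted rank sum test in a randomized pilot is legitimate, no statement in the documents is wrong, and every sizeable gain needs r near 0.5, which nothing in the documents supports. Common insulin titration rules and the exclusion of patients needing intravenous insulin could both weaken the link between HbA1c and inpatient glucose. This stands, and it is why the point claims only a cheap improvement.

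The 0.65 SD shift may also be generous. The Insulin Treatment section rests titration on fingerstick values, and the high alarm is set above 400 mg/dl, although the Groups section says management uses both sources. At a 0.2 SD shift and 20 per arm, the noncentrality is 0.2 × √10 = 0.63. By normal approximation, before the covariate's cost, power is about 9.7% unadjusted, 10.2% at r = 0.3 and 11.3% at r = 0.5. So the power gains depend on the assumed effect; with no zeros, the width ratios do not.

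A reader might infer that adjustment helps whenever HbA1c is prognostic. The figures do not bear this out: at 10 per arm it is a slight loss below r of about 0.24, and with many zeros the interval can widen at r = 0.2. A reader might also expect adjustment to repair Aim 1. It would not. There, "POC-FSBG will be measured any time the CGM alarms", and alarms act only where CGM is unblinded. That unequal ascertainment is a separate issue.

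**Conclusion.** The point holds as a low-cost improvement, strongest for Aim 2. HbA1c is collected in everyone and left out of comparisons that it plausibly helps. The true gain cannot be stated, because r, the sample size, the effect size and the share of zeros are all assumptions here. Within the assumed range for Aim 2, the downside is under 1 power point at 20 or 30 per arm and the upside is about 10 points or more if r reaches 0.5. For Aim 3 the gain may be negligible if most patients never exceed 300 mg/dl.

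A reader might infer that the planned test is invalid or biased. The documents do not support that, because allocation is randomized and the test is sound with one value per patient. The plan should state that unit, since this conclusion does not extend to tests on pooled CGM readings.

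**What to change.** **Aim 2.** Define one value per patient: percent of CGM time above 180 mg/dl. Pre-specify, as the single governing test, the arm coefficient in a regression of outcome rank on arm and HbA1c rank. Report the planned Wilcoxon test as a sensitivity analysis only, so that there is no choice between two p-values. Give the HbA1c-adjusted mean difference in percent time with its model-based 95% interval, labelled descriptive and not used to decide significance.

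**Aim 3.** Also use one value per patient. Keep the unadjusted Wilcoxon test governing and give the HbA1c-adjusted rank analysis as supportive. Report the proportion with any time above 300 mg/dl in each arm, with a Newcombe 95% interval for the difference. At 20 per arm that interval covered 93.6% (50% versus 26%) and 95.7% (30% versus 12%), with mean full widths of 53 and 48 points, so it will be wide.

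**HbA1c rules.** Use only samples drawn before randomization; the protocol does not state the order. Keep patients with a missing value by single imputation from the pooled sample, without regard to arm.

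**Cost.** A few lines of text and one degree of freedom, with no added patient burden. If HbA1c is not prognostic, the interval is about 1.5% wider at 20 per arm and about 3% wider at 10 per arm.
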